7.7. Overdose

Overdose, as defined for this protocol, applies to protocol-required dosing of the investigational product(s) (IPs) only. Therefore, for a drug to be subject to the overdose definition it must be *both required and an investigational drug*. In this study the only required and investigational drug is apremilast and the control arm drug (ie, placebo), hence overdose definition will apply to only apremilast (or matching placebo). Other required or optional non-study drugs intended for prophylaxis of certain side effects, etc, are excluded from this definition.

Overdose for this protocol, on a per dose basis, is defined as ingestion of 4 or more 30 mg apremilast (or matching placebo) tablets in any 24-hour period, whether by accident or intentionally. On a schedule or frequency basis, an overdose is defined as dosing more than 4 times during any 24-hour period.

Adverse Events associated with an overdose must be collected on the Adverse Events page of the eCRF (see Section 10.1) for all overdosed subjects, but the overdose itself is not considered an AE.

Approved

8. CONCOMITANT MEDICATIONS AND PROCEDURES

8.1. Permitted Concomitant Medications and Procedures

Subjects may take any medication that is not restricted by the protocol and would not be expected to interfere with the conduct of the study or affect assessments. Chronic medication should be dosed on a stable regimen.

All medications (prescription and non-prescription), treatments, and therapies taken by the subject from signing the informed consent throughout their entire participation in the study, including those initiated prior to signing the informed consent and continued through the start of the study, must be recorded on the subject's source document and on the appropriate page of the eCRF. The dose, unit, frequency, route, indication, the date the medication was started, and the date the medication was stopped (if not ongoing) must be recorded.

During the study, the initiation of new concomitant medications or a change of existing concomitant medications may potentially indicate the presence of a new adverse event or the worsening of an existing condition. If appropriate, such events should be recorded in the eCRF.

The following topical therapies will be permitted throughout the study:

- Unmedicated skin moisturizers will be permitted for body lesions only.
 - Permitted skin moisturizers may not contain urea or salicylic acid.

8.2. Concomitant Medications Not Recommended

Co-administration of the strong cytochrome P450 3A4 (CYP3A4) enzyme inducer, rifampicin, resulted in a reduction of systemic exposure of apremilast, which may result in a loss of efficacy of apremilast. Therefore, the use of strong CYP3A4 enzyme inducers (eg, rifampicin, phenobarbital, carbamazepine, phenytoin and St. John's Wort) with apremilast is not recommended during the study.

8.3. Prohibited Concomitant Medications and Procedures

The following psoriasis medications cannot be administered for the duration of the study.

- Topical therapy
 - Topical therapy, unless otherwise specified in Section 8.1 (including, but not limited to topical corticosteroids, retinoids or Vitamin D analog preparations, tacrolimus, pimecrolimus, coal tar, anthralin/dithranol, or urea- and salicylic acid-containing moisturizers)
- Conventional systemic therapy
 - Conventional systemic therapy including but not limited to cyclosporine, methotrexate, retinoids, mycophenolate, thioguanine, hydroxyurea, sirolimus, sulfasalazine, azathioprine, fumaric acid esters, and corticosteroids
- Biologic agents, including:

- Adalimumab, etanercept, infliximab, or certolizumab pegol, ustekinumab, secukinumab, ixekizumab, brodalumab, guselkumab, tildrakizumab
- Phototherapy
 - Ultraviolet light B (UVB) or psoralens and long-wave ultraviolet radiation (PUVA)
- Use of any investigational drug or device
- Use of tanning booths, which may confound the ability to interpret data from the study.

8.4. Required Concomitant Medications and Procedures

Not applicable.

Approved

9. STATISTICAL CONSIDERATIONS

9.1. Overview

The objective of this study is to evaluate the health-related quality of life, efficacy, and safety of apremilast compared to placebo, for 16 weeks, and evaluate the long-term effects of apremilast on quality of life, efficacy, and safety for up to 52 weeks in subjects with manifestations of plaque psoriasis and impaired quality of life.

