6.5.4. Psychiatric Evaluation

Treatment with apremilast is associated with an increase in adverse reactions of depression. Before using apremilast in subjects with a history of depression and/or suicidal thoughts or behavior, the Investigator should carefully weigh the risks and benefits of treatment with apremilast in such patients. Subjects should be advised of the need to be alert for the emergence or worsening of depression, suicidal thoughts or other mood changes, and if such changes occur to contact the Investigator.

If a patient suffers from new or worsening psychiatric symptoms, or suicidal ideation is identified, it is recommended to discontinue the subject participation to the study. Subjects who are identified by the Investigator as having attempted suicide must be immediately withdrawn from the study (see Section 11).

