6.5.5. Severe Diarrhea, Nausea and Vomiting

There have been post-marketing reports of severe diarrhea, nausea, and vomiting associated with the use of apremilast. Most events occurred within the first few weeks of treatment. In some cases, patients were hospitalized. Patients 65 years of age or older and patients taking medications that can lead to volume depletion or hypotension may be at a higher risk of complications. Subjects should be monitored for severe diarrhea, nausea and vomiting. If patients develop severe diarrhoea, nausea, or vomiting, discontinuation of treatment may be necessary (see Section 11).

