9.7. Safety Analysis

The safety analyses will be performed using the safety population as defined in Section 9.2, defined as all subjects who are randomized and receive at least one dose of investigational product. Safety will be assessed by clinical review of all relevant parameters including treatment-emergent adverse events (TEAEs), laboratory tests, and vital signs; no inferential testing for statistical significance will be performed. Data from safety assessments will be summarized descriptively for the Placebo-controlled Phase (Weeks 0 to 16) and the Apremilast Exposure Period when subjects receive apremilast treatment. For safety analyses in the Placebo-controlled Phase, baseline will be relative to the first dose date following randomization at Week 0. For safety analyses in Apremilast Exposure Period, baseline will be relative to the first apremilast dose date at Week 0 for subjects initially randomized to apremilast or Week 16 for subjects initially randomized to placebo and switched to apremilast in the Apremilast Extension Phase (Weeks 16-52).

Adverse events will be classified using the Medical Dictionary for Regulatory Activities (MedDRA) classification system. Adverse events will be tabulated by study phase (Double-blind Placebo-controlled Phase or apremilast Exposure Phase). All treatment-emergent adverse events (AEs) will be summarized by system organ class, preferred term, severity, and relationship to IP. Adverse events leading to death or to discontinuation from treatment and serious AEs will also be summarized and listed separately.

Laboratory data will be summarized using shift tables showing the number of subjects with low, normal, and high values based on the normal ranges, pretreatment versus post-treatment.

Vital sign measurements, including weight, will be summarized by visit descriptively (count, mean, median, standard deviation, and range). In addition, shift tables showing the number of subjects with values below, within and above the normal reference ranges pretreatment versus post-treatment will be provided.

The changes and percent changes in body weight will be summarized by visit. In addition, the changes by baseline body mass index (BMI; (< 18.5, 18.5 to < 25, 25 to < 30, 30 to < 35, 35 to < 40, \geq 40 kg/m²) will be explored.

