3.2. Secondary Objectives

The secondary objectives are:

- To assess the efficacy and safety of Apremilast compared to placebo in patients with manifestations of plaque psoriasis and impaired quality of life at Week 16
- To assess the long-term effects of Apremilast with respect to quality of life, efficacy, and safety at Weeks 32 and 52

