4.4. Sample Size Determination

For the primary endpoint, i.e., the response rate (π) defined as the proportion of subjects achieving a ≥ 4 -point reduction from baseline in DLQI at Week 16, the superiority of Apremilast 30 mg BID versus placebo will be tested. The hypotheses on superiority are defined as:

$$H_0: \pi_{APR} - \pi_{PBO} = 0$$

versus

$$H_1: \pi_{APR} - \pi_{PBO} > 0$$

Using an exploratory analysis on a subset of subjects meeting the following criteria: a) ScPGA ≥ 3 or b) NAPSI ≥ 1 or c) PPPGA ≥ 3 at baseline and DLQI ≥ 10 at baseline in the PSOR-008 and PSOR-009 Phase 3 studies, it was estimated that the proportion of subjects who achieved a ≥ 4 -point reduction from baseline in DLQI was 0.50 (97 responders out of 193 subjects) and 0.83 (337 responders out of 406 subjects) for placebo and Apremilast 30 mg BID, respectively.

Assuming a placebo DLQI responder proportion of 0.50 at Week 16, a minimum total sample size of 210 subjects (140 allocated to Apremilast 30 mg and 70 allocated to placebo) is needed to detect a 0.20 difference in the DLQI responder rate between Apremilast and placebo with at least 0.807 power using a two-sided test at the 0.05 level of significance. This sample size calculation is based on an unpooled variance, and determined using the commercial software EaST, Version 6.3. Allowing for an 24% discontinuation rate prior to Week 16, the sample size of 276 subjects should be sufficient.

5. GENERAL STATISTICAL CONSIDERATIONS**5.1. Reporting Conventions**

- The statistical test on the primary endpoint is at a 2-sided 0.05 significance level, any p-values reported for other endpoints are considered as summary statistics;
- P-values are rounded to 4 decimal places. P-values that round to 0.0000 are presented as '<0.0001' and p-values that round to 1.000 are presented as '>0.9999';
- Confidence intervals (CIs) are presented as 2-sided 95% CIs;
- Summary statistics consist of the number and percentage of subjects in each category for discrete variables, and the sample size, mean, median, Standard Deviation (STDEV), minimum, and maximum for continuous variables;
- All mean and median values are formatted to one more decimal place than the measured value, standard deviation values are formatted to two more decimal places than the measured value, minimum and maximum values are presented to the same number of decimal places as the measured value, and the 95% CI are formatted to two more decimal places than the measured value;

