10. SAFETY ANALYSIS

Safety will be assessed via descriptive statistics and point estimates on observed data.

All safety analyses described in this section will be performed for both the Placebo-controlled Phase and the Apremilast Exposure Period. The safety analyses for the Placebo-controlled Phase will be based on the safety population and presented by treatment arm (placebo, and Apremilast 30 mg BID). The safety analyses for the Apremilast Exposure Period will be based on the Apremilast Exposure Population and presented by Apremilast dose group (i.e., Apremilast 30 mg BID) irrespective of the start time of Apremilast exposure (at Week 0 or 16). In addition, selected summaries on AEs for the Observational Follow-up Phase will be listed.

For the analyses of AEs and laboratory marked abnormalities, both subject incidence and exposure-adjusted incidence rate (EAIR) per 100 subject-years for the Placebo-controlled Phase (Weeks 0 to 16) and for the Apremilast Exposure Period will be provided. The point estimates of subject incidence and EAIR are distinguished as following:

- Subject incidence: is defined as the number of subjects with the specific event divided by the number of subjects included in the analysis (i.e., percentage [%] used in a frequency summary). Subjects with multiple occurrences of the specific event in the specific analysis period will be counted only once in the numerator.
- Exposure-adjusted incidence rate (EAIR) per 100 subject-years: The EAIR per 100 subject-years is defined as 100 times the number of subjects with the specific event divided by the total exposure time (in years) among subjects included in the analysis. Subjects with multiple occurrences of the specific event in the specific analysis period will be counted only once in the numerator. The exposure time for a subject without the specific event is the treatment duration (i.e., last dose date-first dose date+1), whereas the exposure time for a subject with the specific event is the treatment duration up to the start date (inclusive) of the first occurrence of the specific event. The total exposure time in years is calculated by dividing the sum of exposure time in days over all subjects included in the analysis by 365.25. The EAIR per 100 subject-years is interpreted as the expected number of subjects with at least one occurrence of the specific event per 100 subject-years of exposure to the IP.

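### Safety against placebo is an objective, but the SAP plans no between-arm difference or interval for adverse events and no subject-once count of the depression and gastrointestinal harms the protocol names

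*Protocol*

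**What the plan says.** The objective is comparative. Protocol 9.1 aims "to evaluate the health-related quality of life, efficacy, and safety of apremilast compared to placebo, for 16 weeks", and SAP 3.2 lists as a secondary objective "To assess the efficacy and safety of Apremilast compared to placebo in patients with manifestations of plaque psoriasis".

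The endpoint and method are descriptive. Protocol Table 2 defines the adverse-event endpoint as the frequency and incidence rate of TEAEs by organ class, preferred term, severity and relationship. Protocol 9.7 summarises safety descriptively and adds that "no inferential testing for statistical significance will be performed". SAP 10 states: "Safety will be assessed via descriptive statistics and point estimates on observed data". It then defines subject incidence and the exposure-adjusted incidence rate (EAIR), each as a quantity within one group. SAP 10.1.1 to 10.1.3 list the tables: overall categories, organ class and preferred term, serious and drug-related events, events leading to interruption or withdrawal, and maximum severity.

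The protocol singles out some harms. Section 6.5.4 says: "Treatment with apremilast is associated with an increase in adverse reactions of depression". Section 6.5.5 says: "Subjects should be monitored for severe diarrhea, nausea and vomiting". Footnote f to the Table of Events directs adverse-event review to psychiatric symptoms, suicidal ideation or attempt, the three gastrointestinal events, and unexplained weight loss.

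**The concern.** Weeks 0 to 16 are the only randomised comparison of safety. From Week 16 every subject receives apremilast, and the Apremilast Exposure Period outputs have a single arm. The SAP gives treatment differences with 95% intervals for the primary endpoint, for the secondary endpoints at Week 16 and for each DLQI subgroup. It gives none for any adverse event.

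The second gap is harder for a reader to repair. Depression and suicidality can be coded to several preferred terms. Diarrhoea, nausea and vomiting are separate terms, and one subject may have more than one of them. The organ-class row counts each subject once but mixes in unrelated events. The planned tables therefore do not show how many subjects in each arm had either named harm. If the grouping is chosen after unblinding, the choice of terms is open to selection.

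**Working it through.** **1. Is a between-arm estimate planned anywhere for adverse events?** SAP 10 to 10.1.4 names subject incidence, EAIR, tables by severity and subgroup, and listings. None is a difference or a ratio, and none has an interval. The only interval text that could reach safety is the reporting convention in SAP 5.1, "Confidence intervals (CIs) are presented as 2-sided 95% CIs". That sets the format of intervals and assigns none to an adverse-event output.

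**2. Can the grouped counts be recovered from the planned tables?** If three preferred-term rows show a, b and c subjects, the number with at least one event lies between max(a, b, c) and a + b + c. With illustrative counts of 18, 9 and 4 out of 184, it is between 18 (9.8%) and 18 + 9 + 4 = 31 (16.8%). The organ-class row may lower the upper bound but does not fix the number. The by-subject listings would allow a count, but no planned table gives it.

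**3. How precise would the contrast be?** Neither document gives a figure for safety precision, so there is none to reproduce. Inputs:
- Arm sizes: SAP 4.1 and 4.4 plan 276 subjects at 2:1, that is 184 and 92. Protocol 9.3 plans 255, that is 170 and 85. All randomised subjects are assumed to be dosed.
- Incidences: the documents give none, so these are assumptions.

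Newcombe interval, with d = pA - pP and Wilson limits (lA, uA) and (lP, uP):
- lower = d - sqrt[(pA - lA)² + (uP - pP)²]
- upper = d + sqrt[(uA - pA)² + (pP - lP)²]

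For 3% versus 1% at 184:92, the Wilson limits are 1.34 to 6.58% and 0.17 to 5.76%.
- lower = 2.0 - sqrt(1.66² + 4.76²) = 2.0 - 5.04 = -3.0 points
- upper = 2.0 + sqrt(3.58² + 0.83²) = 2.0 + 3.68 = +5.7 points

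| Assumed incidence | 184:92 | 170:85 |
|---|---|---|
| 3% vs 1% | -3.0 to +5.7 | -3.4 to +5.9 |
| 5% vs 3% | -4.2 to +6.6 | -4.6 to +6.8 |

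With whole counts at 184:92:
- 3 versus 0 gives +1.6 (-2.5 to +4.7)
- 9 versus 2 gives +2.7 (-3.2 to +7.1)
- 37 versus 9 gives +10.3 (+1.0 to +18.2)

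**4. Why a score interval?** The Wald half-width is 1.96 × sqrt[pA(1 - pA)/184 + pP(1 - pP)/92]. It gives ±3.2 points at 3% versus 1% and ±4.7 at 5% versus 3%. At 1% of 92 fewer than one placebo event is expected (0.92), and the Wald interval is too narrow: 6.4 points in total against 8.7 for Newcombe.

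**The case against.** The strongest reply is that nothing promised is missing. Table 2 defines the safety endpoint as frequency and incidence rate, Protocol 9.7 prescribes descriptive summaries, and the SAP supplies them by arm. A reader might infer that the SAP contradicts the objective or fails to deliver its endpoint. The documents do not support that: endpoint, protocol method and SAP method agree.

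A reader might also infer that the tables hide precision behind bare percentages. They do not. SAP 5.1 requires counts with percentages and the population size on every table, so a crude interval can be worked out for any single row. Nor are the named harms ignored. SAP 10.1.3 tabulates each preferred term by maximum severity, so severe diarrhoea, severe nausea and severe vomiting each appear by arm. Serious events and withdrawals have their own tables, and weight change has categorical tables in SAP 10.3. Protocol 6.5.4 and 6.5.5 are monitoring instructions and do not require a composite analysis.

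Finally, intervals across many terms invite readers to treat exclusion of zero as a test, which sits uneasily with 9.7. That counts against an interval for every preferred term. It does not rule out a short list: 9.7 bars significance testing, and a difference with an interval and no p-value is estimation.

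What remains is that no contrast is pre-specified, and the grouped harms cannot be counted from any planned table.

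**Conclusion.** The point holds as a worthwhile, low-cost improvement. The SAP meets its descriptive endpoint, but it leaves the comparative safety objective without an estimate of the contrast or its uncertainty. It also leaves the two named groups of harms without a subject-once count. At the planned sizes an assumed 9 versus 2 events is compatible with no excess and with an excess of about 7 points, and a side-by-side table does not say so.

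The absence of a difference, an interval and a grouping is read directly from SAP 10 and depends on no number. The interval widths rest on assumed incidences and on all randomised subjects being treated; they show scale only. The primary efficacy result and its type I error are unaffected.

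**What to change.** In SAP 10.1, for the Placebo-controlled Phase on the safety population:

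1. Add two grouped rows, each counting a subject once, with preferred-term lists fixed before the Week 16 unblinding: any depression or suicidality term; and any diarrhoea, nausea or vomiting, shown for all severities and for severe events.
2. For these rows and the overall TEAE categories in SAP 10.1.1, report the risk difference (apremilast minus placebo) with a 95% score interval, Newcombe or Miettinen-Nurminen. Give no p-values, and label the intervals descriptive and unadjusted for multiplicity.

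Intervals for each preferred term in the 5% table are optional.

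The cost is SAP wording, two term lists and minor programming. The data are already collected, and SAP 2 places finalisation before the Week 16 transfer. No visit, sample size or protocol rule changes. The downside is a few unadjusted intervals that could be over-read, which the labelling should limit. If the Week 16 data have already been unblinded, the groupings should be reported as post hoc.

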9.2. Study Population Definitions

Four analysis populations will be defined for this study. These populations include the safety population, the intent to treat (ITT) population, the per protocol (PP) population, and the apremilast exposure population.

- The Safety population will consist of all subjects who are randomized and receive at least one dose of investigational product (IP). This set of subjects will be included in the treatment group corresponding to the IP they actually receive. This will be the population for all safety analyses on data from the Placebo-controlled Phase.
- The ITT population will consist of all subjects who are randomized. This will be the primary population for the primary endpoint and all other quality of life and efficacy analyses. Baseline summaries will also be based on the ITT population.
- The PP population will consist of all subjects who are in the ITT population, complete the Placebo-controlled Phase, and have no major protocol violations. The PP population will only be used to supplement the primary endpoint ITT analysis.
- The apremilast (APR) exposure population will consist of only those subjects who receive at least one dose of apremilast treatment. The APR exposure population will only be used for the purposes of safety reporting including all safety data during apremilast treatment.

9.3. Sample Size and Power Considerations

Using an exploratory analysis on a subset of subjects meeting the following criteria: 1) ScPGA \geq 3 at baseline or 2) NAPSI \geq 1 at baseline or PPPGA \geq 3 at baseline and DLQI \geq 10 at baseline in the PSOR-008 and PSOR-009 Phase 3 studies, it was estimated that the proportion of subjects who achieved a \geq 4-point reduction from baseline in DLQI was 0.50 (97 responders out of 193 subjects) and 0.83 (337 responders out of 406 subjects) for placebo and apremilast 30 mg, respectively.

Assuming a placebo DLQI Responder proportion of 0.50 at Week 16, a minimum total sample size of 210 subjects (140 allocated to apremilast 30 mg and 70 allocated to placebo) is needed to detect a 0.20 difference in the DLQI Responder proportions between apremilast and placebo with at least 0.807 power using a two-sided test at the 0.05 level of significance. This sample size calculation is based on an unpooled variance, and was determined using the commercial software EaST, Version 6.3. Allowing for a 18% discontinuation rate prior to Week 16, the sample size was revised from a total of 210 subjects to a final sample size of 255. If there are no discontinuations prior to Week 16, then the power with a sample size of 255 subjects would

Approved

increase to 0.872. Hence when addressing missing data due to discontinuations with multiple imputations, we would expect the power to be in between the bounds of 0.807 (based on 210 subjects) and 0.872 (based on 255 subjects), as the analysis that incorporates multiple imputation under a missing at random assumption will always be more efficient compared to the observed analysis when the missing data is actually missing completely at random.

